[figure not shown]
[figure not shown]

[figure not shown]
TITLE PAGE

Protocol Number:	NAV-17A-008
Title:	An Open-Label, Single-Group Study to Evaluate the Efficacy and Safety of SPN-820 in Adults With Major Depressive Disorder
Sponsor:	Navitor Pharmaceuticals, Inc. [name] Office: [contact] [contact]
IND Number:	155072
Investigational Medicinal Product:	NV-5138 SPN-820 (Supernus Pharmaceuticals, Inc. product alternative identification number)
Indication:	Major Depressive Disorder

Phase:	2
Protocol Version:	3.0
Amendment:	Not applicable
Date:	14 February 2024
Good Clinical Practice Statement:	This study is to be performed in full compliance with the International Council for Harmonisation Good Clinical Practices and all applicable local regulations. All required study documentation will be archived as required by regulatory authorities.

CLINICAL PROTOCOL SYNOPSIS**Sponsor:** Navitor Pharmaceuticals, Inc.**Investigational Medicinal Product:** NV-5138
SPN-820 (Supernus Pharmaceuticals, Inc.
alternative product identification number)**Name of Active Ingredient:**
(S)-2-amino-5,5-difluoro-4,4-dimethylpentanoic acid**Protocol Number:** NAV-17A-008**Phase of Development:** 2**Study Title:** An Open-Label, Single-Group Study to Evaluate the Efficacy and Safety of SPN-820 in Adults With Major Depressive Disorder**Number of Study Sites:** Up to 6 investigational sites are planned in the United States (US)**Number of Subjects:** Approximately 50 subjects will be enrolled to achieve approximately 40 subjects completed.**Indication:** Major Depressive Disorder (MDD)**Objectives:**Primary Objective:

- To evaluate the efficacy of SPN-820 administered once every 3 days for a 7-day treatment period in adults with MDD.

Secondary Objectives:

- To evaluate the safety and tolerability of SPN-820 administered once every 3 days for a 7-day treatment period in adults with MDD.
-

Exploratory Objective:

- To characterize the effect of SPN-820 on brain-derived neurotrophic factor (BDNF) concentrations.

Endpoints:Primary Endpoint:

- Change from baseline to each time point in the Hamilton Depression Rating Scale-6 Items (HAM-D₆) total score.

Secondary Efficacy Endpoints:

- Change from baseline to each time point in the Montgomery–Åsberg Depression Rating Scale (MADRS) total score.
- Change from baseline to each time point in the Clinical Global Impression – Severity of Illness (CGI-S) total score.
- Proportion of subjects achieving a $\geq 50\%$ reduction from baseline in the MADRS total score.
- Proportion of subjects in remission (MADRS total score ≤ 10) at each time point.

- Percentage of subjects with a CGI-S score of 1 or 2 at each time point.
- 

Safety Endpoints:

- Treatment-emergent adverse events (TEAEs).
- Clinical safety laboratory test results.
- Vital sign measurements including orthostatic blood pressure and pulse rate.
- Body weight.
- Electrocardiography (ECG) findings.
- Physical examination findings.
- Suicidal ideation and behavior as measured by the Columbia Suicide Severity Rating Scale (C-SSRS) score.
- Dissociative symptomatology as measured by Clinician-Administered Dissociative State Scale (CADSS) score.
- Psychopathology severity as measured by Brief Psychiatric Rating Scale Positive Subscale (BPRS+) score.

Exploratory Endpoint:

- Change from baseline to each time point for BDNF concentrations.

Study Design:

This is an open-label study of SPN-820 administered orally every 3 days for a 7-day treatment period in adult subjects with MDD. The study consists of a 28-day screening period, a 10-day evaluation period (clinic and home), and a safety follow-up phone call approximately 5 (+2) days after the last administration of study medication (SM).

To be eligible, subjects must be taking 1 approved antidepressant medication (i.e., an approved therapy for depression; [Appendix 11.2](#)) at a stable dosage for a minimum of 6 weeks before the screening visit. If a subject is taking a second antidepressant or an augmentation therapy, the investigator will decide the appropriate medication that should be discontinued. The second medication should be discontinued for at least 5 half-lives before baseline. In addition, subjects must maintain a MADRS total score ≥ 22 , a CGI-S score ≥ 4 , and a detectable level of antidepressant therapy (ADT) during the screening period to be eligible. If the MADRS total scores vary $\geq 25\%$ between the highest and lowest score from screening to baseline (Day 1), subjects will be excluded. All subjects who meet the eligibility criteria will take 2400 mg (six 400 mg capsules) of SPN-820 orally and continue their ADT at a stable and therapeutic dose while in the study.

The evaluation period includes 4 clinic visits (on days 1, 4, 7 and 10). Subjects will receive SM at the clinic on days 1, 4 and 7. Subjects will not receive SM on days 2, 3, 5, 6, 8, 9 and 10. Subjects will continue their ADT throughout the study. All safety, efficacy, , and pharmacodynamic (PD) assessments and procedures will be performed as outlined in [Table 1](#) and [Table 2](#).

At the end of study (EOS; Day 10) or early termination (ET), if applicable, subjects will return to the clinic for the EOS visit. Approximately 5 days (+2 days) after the last administration of SM (Day 7) and once all study visits are completed; subjects will receive a safety follow-up phone call. Subjects who discontinue the study due to adverse events (AEs) will be followed for at least 30 days following the date of last administration of SM or until resolution, or until, in the medical judgment of the investigator, the event has stabilized or is assessed as chronic.

Duration of Subjects' Participation:

The total study duration for each subject's participation is up to 40 days (screening period [up to 28 days], evaluation period [10 days], and safety follow-up phone call [5 days from Day 7]).

Investigational Medicinal Products, Reference Therapy, Doses and Mode of Administration:

Study Medication: SPN-820 400 mg capsules

Dosage: 2400 mg (six 400-mg capsules) administered once a day every 3 days

Mode of Administration: Oral, as intact capsules, in the morning approximately 3 hours after breakfast

Sampling for [REDACTED] Pharmacodynamic Assessments:

[REDACTED]
[REDACTED]
[REDACTED].

Seven total blood samples will be collected for measurement of BDNF concentrations: 3 pre-dose collections on days 1, 4, and 7; 3 post-dose collections 4 hours after SM administration on days 1, 4, and 7; and 1 collection on Day 10.

Statistical Methodology:

Sample Size: Approximately 50 subjects will be enrolled to achieve approximately 40 subjects completed. This sample size is based on clinical judgment without a power calculation.

Analysis Populations:

The full analysis set (FAS) includes all subjects who receive at least one dose of SM and have a baseline and at least one post-baseline measurement of HAM-D₆.

The safety population includes all subjects who receive at least one dose of SM.

[REDACTED]
[REDACTED].

The PD population includes subjects who receive at least one dose of SM and have a baseline and at least one post-baseline BDNF concentration.

Statistical Methods: Continuous variables will be summarized using descriptive statistics (i.e., number of subjects, mean, standard deviation, median, interquartile range [Q1 and Q3], minimum and maximum values). Categorical variables will be summarized with counts and percentages.

The efficacy, safety, [REDACTED] and PD endpoints will be analyzed descriptively using the FAS, safety, [REDACTED] and PD populations, respectively. Unless otherwise specified, no missing data will be imputed. Details of data analyses will be described in the statistical analysis plan.

Inclusion Criteria:

1. Is a male or female subject, aged 18 to 65 years (inclusive) at screening.
2. Capable of giving signed informed consent, able to understand and comply with protocol requirements, instructions, and protocol-related restrictions, and likely to complete the study as planned.
3. Has a body mass index 19.0 to 40.0 kg/m² (inclusive).
4. Is able to swallow each capsule whole, without crushing, chewing, or opening.
5. Has a current diagnosis of MDD according to the Diagnostic and Statistical Manual of Mental Disorders, 5th Edition (DSM-5) for either recurrent or single episode MDD without psychotic features that is confirmed by the Mini International Neuropsychiatric Interview (MINI) at screening.
6. Has a MADRS total score of ≥ 22 for the current major depressive episode (MDE) at screening and baseline (Day 1) before SM administration.
7. Has a CGI-S score of ≥ 4 (moderately ill or worse) at screening and baseline (Day 1) before SM administration.
8. Has been on a stable, therapeutic dose of one of the following study-approved ADTs for the current MDE for ≥ 6 weeks prior to screening: citalopram, escitalopram, paroxetine, fluoxetine, sertraline, duloxetine, venlafaxine (immediate release or extended release), desvenlafaxine, vilazodone, levomilnacipran, vortioxetine, bupropion, or dextromethorphan/bupropion. Subject must be on antidepressant monotherapy before baseline.

Note: If a subject is taking a second ADT or augmentation therapy at screening, the investigator should decide if it is medically appropriate to discontinue the second drug before baseline. If so, the second drug should be discontinued for at least 5 half-lives prior to baseline. If not, the subject should be excluded from the study.

9. Agrees to maintain a stable therapeutic dose of the approved ADT throughout the study.
10. Non-pregnant female subjects of childbearing potential (FOCP) who are exclusively in a same-sex relationship are included without the need of acceptable birth control methods.

FOCP who are sexually active with a male partner (who is biologically capable of having children), must agree to use one of the following acceptable birth control methods after signing the informed consent form (ICF), throughout the study, and for 30 days following the last dose of SM:

- a. Simultaneous use of male condom and intra-uterine contraceptive device placed at least 4 weeks prior to the first administration of SM.
- b. Simultaneous use of a male condom and diaphragm with spermicide.
- c. Established hormonal contraceptive (started at least 4 weeks prior to the first dose of SM).

Female subjects are considered to be not of childbearing potential if they are either postmenopausal (amenorrhea for at least 2 years and serum follicle-stimulating hormone level of >40 IU/L) or permanently sterilized (e.g., bilateral tubal ligation, bilateral oophorectomy, or bilateral salpingectomy etc.) for a minimum of 6 months prior to screening.

All FOCP must have a negative serum pregnancy test result before administration of SM.

11. Male subjects
 - a. Who have been surgically sterilized (6 months minimum) prior to Screening visit are eligible to participate without any contraception.
 - b. Who are biologically capable of having children and have female partners of childbearing potential must use one or more methods of contraception as stated in IC #10 which must be used from the time of signing the ICF until 90 days after the last dose of SM.

- c. Who are exclusively in a same-sex relationship or have female partners considered not to be of childbearing potential are required to use a condom from the first administration of SM through 7 days after the last administration of SM.

All male subjects must refrain from donating sperm from the first administration of SM until 90 days after the last administration of SM.

Exclusion Criteria:

- 1) Has a MADRS total score improvement of $\geq 25\%$ from the highest to the lowest score from screening to baseline.
- 2) Has been treated with electroconvulsive therapy, transcranial magnetic stimulation, or vagal nerve stimulation for the current MDE within 6 months prior to screening.
- 3) Has received treatment with long-acting injectable antipsychotics within 3 months prior to screening.
- 4) Has demonstrated a non-response to esketamine or off-label use of ketamine; or has taken esketamine or ketamine < 6 months prior to screening.
- 5) If treated with trazodone, is unable to discontinue treatment with doses > 150 mg daily for a minimum of 5 half-lives before baseline.
Note: trazodone ≤ 150 mg/day for sleep is permitted as needed if the subject has been taking the same low dose of trazodone for insomnia for at least 3 months.
- 6) Has unstable hypothyroidism. If the thyroid-stimulating hormone value is out of range (> 4.0 mIU/L), regardless of thyroid history, a free thyroxine (FT4) will be measured. If the FT4 value is abnormal (levels < 0.8 mIU/L) and considered to be clinically significant (after discussion with the Medical Monitor), the subject will not be eligible.
Note: treatment with thyroid hormones is allowed if taken at a stable dose for ≥ 3 months and the subject's thyroid levels are normal.
- 7) Has clinically significant abnormal laboratory profiles (alanine aminotransferase or aspartate aminotransferase values $\geq 3 \times$ the upper limit of normal [ULN] or total bilirubin $\geq 1.5 \times$ ULN), vital sign measurements, or ECGs prior to baseline, per investigator judgment (see **Note** below). If there are any abnormalities that are not specified in the inclusion and exclusion criteria, the investigator must determine their clinical significance and record it in the subject's source documents.
- 8) Has abnormal renal function as demonstrated by an estimated glomerular filtration rate ≤ 60 mL/min according to the Chronic Kidney Disease Epidemiology Collaboration equation (CKD-EPI) equation at screening and baseline.
- 9) Has a history of substance use disorder within 6 months prior to screening or is currently using or has a positive result (urine drug screen) at screening or baseline for drugs of abuse (except for cannabis, see exclusion 11).
- 10) Has a history of alcohol use disorder within 6 months prior to screening. A subject who has a positive alcohol test result at screening and, if based on the investigator's opinion the subject does not have a history of alcohol use disorder, the subject may continue to the baseline visit. Subjects who have a positive alcohol test result at baseline will be excluded. Subjects should refrain from using alcohol during the study. Subjects who have a positive alcohol test result on days 1, 4, or 7 will be withdrawn from the study.
- 11) Has a diagnosis of cannabis use disorder within 6 months before screening and has a positive urine drug screen for cannabis at screening.
 - a. At the discretion of the Sponsor, recreational use (not daily) is allowed and should be kept consistent during the study. Subjects must agree to refrain from using cannabis 48 hours prior to the clinic visits.
 - b. Medical cannabis prescribed for a medical condition (e.g., muscle spasms, nausea, vomiting, pain) other than depression and seizures is allowed if taken at a stable regimen for at least 3

months prior to screening ([Appendix 11.1.1](#)). Newly prescribed cannabis treatment and/or a change to the existing regimen are/is prohibited. When applicable, subjects should show proof of their prescription for medical cannabis.

- 12) Has had any suicidal behavior or suicidal ideation of type 4 (active suicidal ideation with some intent to act, without specific plan) or type 5 (active suicidal ideation with specific plan and intent) based on the C-SSRS in the 1 year before screening; a history of suicide attempt in the last 2 years; or more than 2 lifetime suicide attempts.
- 13) Has a lifetime history of psychotic disorder, including but not limited to schizophrenia, MDD with psychotic features, or bipolar I/II disorder with and without psychotic features.
- 14) Has a diagnosis within the last 12 months before screening or current diagnosis of post-traumatic stress disorder, obsessive-compulsive disorder, panic disorder, acute stress disorder, or has a history of intellectual disability, autism, or cluster A or B personality disorder (per DSM-5 criteria).
 - a. Current diagnosis of co-morbid generalized anxiety disorder is allowed but is subject to medication restrictions (anticonvulsants and beta-blockers are allowed if the subject is on a stable regimen for 2 months prior to screening).
 - b. Established attention-deficit/hyperactivity disorder (ADHD) diagnosis is allowed. Subjects must provide confirmation of ADHD diagnosis (i.e., provide medical records for prescribed ADHD medications) and be on a stable dose of ADHD medication for at least 3 months prior to screening.
- 15) Has a history of a psychiatric or neurologic condition or symptoms that could impose undue risk or compromise the study including but not limited to:
 - a. History of seizure disorder or history of epilepsy (except history of absence or uncomplicated childhood febrile seizures).
 - b. History of clinically significant or moderate head trauma that, in the investigator's opinion, is likely to affect central nervous system functioning.
 - c. Has current evidence of delirium or dementia.
- 16) Has a history of cardiovascular, respiratory, gastrointestinal, renal, hepatic, hematologic, or other medical disorder that could impose undue risk or compromise the study, in the investigator's opinion, including but not limited to:
 - a. Cardiovascular:
 - i. Clinically significant symptomatic orthostatic hypotension.
 - ii. Uncontrolled hypertension despite diet, exercise, and antihypertensive medications.
 - iii. Acute coronary syndrome.
 - iv. History of unexplained loss of consciousness, unexplained syncope, unexplained irregular heartbeats.
 - v. QT interval corrected using Fridericia's method ≥ 450 msec (for men) or ≥ 470 msec (for women) at screening (see [Note](#) below).
 - vi. Subject or family history of congenital long QT syndrome.
 - b. Oncological:
 - i. Malignant tumors within 5 years prior, with the exception of benign skin tumors.
 - ii. Diagnosis or family history of tuberous sclerosis complex.
 - c. Positive result for human immunodeficiency virus 1/2 antigen/antibody (HIV 1/2 Ag/Ab), hepatitis B surface antigen (HBsAg) or hepatitis C antibody (HCV Ab) at screening, unless:
 - i. HIV 1/2 Ag/Ab positive: subjects must have an HIV confirmation test. If the confirmatory test is positive, subjects are eligible if they are on chronic suppressive antiviral medication for >6 months with an undetectable viral load at screening.

- ii. HBsAg positive: subjects should be tested for immunoglobulin M antibody to hepatitis B core antigen and hepatitis B surface antibody to detect acute or chronic infection (ineligible). Subjects whose results indicate immunity (either by natural infection or vaccination) with no active infection are eligible.
 - iii. HCV Ab positive: subjects must have undetectable HCV ribonucleic acid to be eligible.
 - d. Unintended recent clinically significant weight loss in the investigator's opinion.
 - e. Has chronic urinary tract infections.
 - f. Blood donation or loss of blood of ≥ 500 mL within 56 days prior to screening.
 - g. Is on any medication that could, in the investigator's opinion, interfere with the assessments of safety, tolerability, or efficacy, or interfere with the conduct or interpretation of the study.
- 17) Requires treatment with a medication or other substance that is prohibited by the protocol (see [Section 5.7.2](#)).
- 18) Has history of severe drug allergy or hypersensitivity, or hypersensitivity to the SM or excipients.
- 19) Female subjects who are pregnant or lactating or planning to become pregnant while enrolled in the study.
- 20) In the investigator's opinion, is unlikely to comply with the protocol or is unsuitable for any other reason.
- 21) Has previously enrolled in a NV-5138 study.
- 22) Is currently participating in another clinical trial or has received an investigational product in another clinical trial within 30 days of screening.
- 23) Is a member of study personnel or of their immediate families or is a subordinate (or immediate family member of a subordinate) to any of the study personnel.

Note: Repeat testing for clinical laboratory parameters, vital signs, and ECG is permitted one time for each test, at the discretion of the investigator, as long as the repeat test result is available within the 28-day screening period to determine eligibility. Repeat testing is not allowed without justification from the study site and agreement from the Medical Monitor and the Sponsor on a case-by-case basis.

Table of Contents

TITLE PAGE	1
INVESTIGATOR'S SIGNATURE PAGE	2
SUPERNUS PROTOCOL APPROVAL PAGE	3
NAVITOR PROTOCOL APPROVAL PAGE	4
CLINICAL PROTOCOL SYNOPSIS	5
1 LIST OF ABBREVIATIONS	15
2 INTRODUCTION	17
2.1 Background	17
2.2 SPN-820	17
2.3 Nonclinical Studies	17
2.4 Clinical Studies	18
2.5 Study Rationale	20
2.6 Summary of Benefits and Risks	21
3 STUDY OBJECTIVES AND ENDPOINTS	22
3.1 Objectives	22
3.2 Endpoints	22
4 INVESTIGATIONAL STUDY PLAN	24
4.1 Overall Study Design and Plan	24
4.2 Study Population	25
4.3 Completion of Study	31
4.4 Discontinuation or Early Termination of Subjects	31
5 STUDY TREATMENT	33
5.1 Study Medication Identity, Packaging, and Labeling	33
5.2 Study Medication Administration	33
5.3 Missed Study Medication Administrations or At-Home Phone Calls	33
5.4 Subjects' Antidepressant Therapy	33
5.5 Method of Assigning Subjects to Treatment	34
5.6 Study Medication Handling and Accountability	34
5.7 Concomitant and Prohibited Medications	35
6 STUDY METHODS	37
6.1 Clinic Study Visits and Procedures	44
6.2 Home Evaluations	47
6.3 Safety Follow-Up Phone Call (Day 12)	48
6.4 Unscheduled Visits	48
6.5 Urine Drug and Alcohol Screen	48
6.6 Pharmacokinetic Blood Sampling	48
6.7 Pharmacodynamic Blood Sampling	49

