5.7.1 Permitted Concomitant Medications

A comprehensive list of permitted medications is shown in [Appendix 11.1.1](#). The list is not all inclusive. Contact the Medical Monitor for any questions related to the subject's current concomitant medication(s). Most of the concomitant medications are allowed if on a stable dose for at least 3 months prior to screening or otherwise specified in [Appendix 11.1.1](#).

- Treatment for hypercholesterolemia (e.g., statins, gemfibrozil) and hyperlipidemia if on a stable dose for ≥ 3 months prior to screening.
- Treatment for hypertension with angiotensin-converting enzyme (ACE) inhibitors, angiotensin receptor blockers, calcium channel blockers, and beta-blockers, alone or in combination with diuretics if on a stable dose for ≥ 2 weeks before screening.
- Inhalers for the treatment of asthma, if the subject has stable, controlled asthma and no changes for ≥ 6 months prior to screening.
- Treatment for diabetes if on a stable dose for ≥ 3 months before screening. Insulin will not be permitted.
- For ADHD treatment, psychostimulants, atomoxetine, guanfacine, and clonidine are allowed, if on a stable dose for ≥ 3 months before screening. Confirmation of ADHD diagnosis will be required.

The stable dose of all concomitant medications permitted in the study **must be maintained** throughout the duration of the study participation.

As needed, the following treatments will also be permitted:

- For sleeping, the following medications are permitted if on a stable dose (dose incrementation is prohibited) for ≥ 4 weeks prior to screening ([Appendix 11.1.1](#)):
 - Hypnotics (e.g., zaleplon and zolpidem).
 - Benzodiazepines: lorazepam (2 mg total daily dose [TDD]), clonazepam (0.5 mg TDD), and flurazepam (30 mg TDD). Benzodiazepines should be taken >12 hours prior to any study visits.

- Trazodone (≤ 150 mg/day) as needed if the subject has been taking the same low dose of trazodone for insomnia for ≥ 3 months.
- Nutritional supplements (e.g., multivitamins, fish oil, melatonin).
- EMLA[®] or other numbing cream for venipuncture.
- Common over-the-counter therapies for minor, transient ailments (e.g., acetaminophen or ibuprofen for headaches, fever, etc.).

All concomitant medications will be recorded in the eCRF.

Subjects must be on a stable dose of 1 study-approved antidepressant medication; a list of these ADTs is provided in [Appendix 11.2](#).

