c. A microscopic examination will be performed on abnormal findings unless otherwise specified.

d. Standard urine drug screen will be performed at screening. A positive test must be confirmed against medical history and concomitant medications.

- e. Amphetamine, methamphetamine, and methylphenidate (methylphenidate will not be tested during the treatment period) positive tests are allowed only for subjects diagnosed with ADHD confirmed by a prescription record. Benzodiazepine positive test is allowed if used for insomnia.
 - f. POC urine drug screen together with the breathalyzer will be performed at baseline (Day 1) and all post-baseline visits (days 4, 7, and 10).
 - g. A serum pregnancy test will be performed at screening; a urine pregnancy test will be performed on days 1, 4, 7, and 10.

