4.2. Protocol Deviations

A protocol deviation is defined as any change, divergence, or departure from the study design or procedures defined in the protocol. An important protocol deviation (IPD) is defined as a protocol deviation that might significantly affect the completeness, accuracy, and/or reliability of the study data or that might significantly affect a subject's rights, safety, or well-being.

Potential IPDs may include, but are not limited to:

- Subjects who received the study treatment but are later found not to have met all the inclusion criteria or met any of the exclusion criteria
- Subjects who received concomitant medications that were prohibited as described in Protocol Section 5.7

Occurrence of any of these and other events may be considered as potential IPDs. However, these events should be categorized as IPDs only if they could potentially affect interpretation of study results. Prior to the database lock, potential IPDs identified in the clinical database and/or recorded in the site deviation log will be reviewed for the determination of IPDs. All protocol deviations will be provided in subject data listings.

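### Exclusion 9 and Section 6.5 omit the drug-screen exceptions granted in Table 3 footnote e, so sites can reach opposite decisions on the same subject

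*Protocol*

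**What the plan says.** Three places in the protocol tell a site what to do with a positive urine drug screen.

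- **Exclusion 9** (synopsis and Section 4.2.3, same wording) excludes a subject who "has a positive result (urine drug screen) at screening or baseline for drugs of abuse (except for cannabis, see exclusion 11".
- **Section 6.5** says that a positive drug screen at baseline or on days 1, 4 or 7 should lead to withdrawal, and that HAM-D6, MADRS and CGI-S should not be done at that visit. It states no exception, not even for cannabis.
- **Table 3 footnote e** (Section 7.4.1) says of amphetamine, methamphetamine and methylphenidate that "positive tests are allowed only for subjects diagnosed with ADHD confirmed by a prescription record". It adds: "Benzodiazepine positive test is allowed if used for insomnia".

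The medication rules admit the people concerned. Exclusion 14b accepts established ADHD and requires such subjects to "be on a stable dose of ADHD medication for at least 3 months prior to screening". Section 5.7.1 says: "For ADHD treatment, psychostimulants, atomoxetine, guanfacine, and clonidine are allowed". The same section and Appendix 11.1.1 permit lorazepam, clonazepam and flurazepam for sleep within stated limits, and Section 5.7.1 requires permitted medication to stay at a stable dose during the study.

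On the analysis side, SAP 4.1 tabulates eligibility criteria met or not met and the reasons for screen failure. SAP 4.2 lists as potential important deviations treated subjects who "are later found not to have met all the inclusion criteria or met any of the exclusion criteria". SAP 3.9.1 summarizes efficacy by observed case, without imputation.

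**The concern.** A subject can follow the medication rules exactly and, because of that, produce a result that one part of the protocol accepts and two other parts do not. Neither Exclusion 9 nor Section 6.5 refers to footnote e. A site working from the numbered criteria screens the subject out, and a site working from the laboratory table enrols the same subject. After enrolment, a site working from Section 6.5 withdraws a subject whom a site working from footnote e keeps.

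Up to 6 sites are planned and the analysis is purely descriptive in a single group of about 50. Differences between sites in who is enrolled and who is rated therefore pass straight into the summaries, with no comparator to absorb them.

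**Working it through.** There is no planned figure to reproduce, so the check compares the texts and then counts ratings.

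**Step 1. Which drugs are tested, and when.** Per Table 3, amphetamines, methamphetamine and benzodiazepines are on the standard panel (screening) and on the point-of-care panel (baseline and later clinic visits). Methylphenidate is on the standard panel only. Cannabinoids are on both.

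**Step 2. Apply each rule to the same result.**

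| Subject and positive result | Exclusion 9 (screening, baseline) | Section 6.5 (baseline, days 1, 4, 7) | Table 3 footnote e |
|---|---|---|---|
| Prescription-confirmed ADHD, amphetamine positive | Excluded | Withdrawn, no efficacy ratings | Allowed |
| Prescription-confirmed ADHD, methylphenidate positive (screening only) | Excluded | Not tested | Allowed |
| Insomnia use of a permitted benzodiazepine, benzodiazepine positive | Excluded | Withdrawn, no efficacy ratings | Allowed |
| Cannabis use permitted by Exclusion 11, cannabinoid positive | Exempt | Withdrawn, no efficacy ratings | Silent |

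The first three rows set Exclusion 9 against footnote e. The first, third and fourth show Section 6.5 in conflict with footnote e or with the cannabis exemption.

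**Step 3. Does footnote e reach past screening?** It is attached to entries in both panels, and it remarks that methylphenidate is not tested during treatment. It was therefore written with the treatment period in view, which is where Section 6.5 operates.

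**Step 4. What one withdrawal costs in primary-endpoint data.** Table 2 schedules these post-baseline HAM-D6 ratings: Day 1, 3 (2, 4 and 8 hours); days 2–3, 2; Day 4, 4 (pre-dose, 2, 4 and 8 hours); days 5–6, 2; Day 7, 4; days 8–9, 2; Day 10, 1.

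- Total: 3 + 2 + 4 + 2 + 4 + 2 + 1 = 18.
- Withdrawn on Day 4: 4 + 2 + 4 + 2 + 1 = 13 lost; 13/18 = 72%.
- Withdrawn on Day 7: 4 + 2 + 1 = 7 lost; 7/18 = 39%.
- Withdrawn on Day 1 before dosing: the subject enters neither the FAS nor the safety set.

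These counts assume that ratings stop at withdrawal. Section 6.5 requires the screen result before any efficacy rating, so the pre-dose rating goes too. Section 4.4 bars efficacy ratings at an early termination visit 72 hours or more after the last dose, so a visit after the Day 4 or Day 7 clinic day would not recover them.

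**Step 5. Weight of one subject.** 1/50 = 2% of planned enrolment; 1/40 = 2.5% of planned completers. How many subjects are involved is not derivable: the documents give no rate of use, no rate of detection and no number to be screened.

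**The case against.** The best defence is that the intent can be recovered. Exclusion 9 is limited to drugs of abuse, and prescribed, documented use can be read as falling outside that phrase. Footnote d says of the screening test: "A positive test must be confirmed against medical history and concomitant medications". Footnote e is the more specific rule, the medication lists agree with it, and sites are told to take medication questions to the Medical Monitor.

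Part of this stands. A reader might infer that Exclusion 9 bars every positive screen apart from cannabis; its wording is narrower than that. The defence still does not remove the conflict, for three reasons. Exclusion 9 handles cannabis, including prescribed medical cannabis through Exclusion 11, by an explicit exemption, so leaving prescribed stimulants and benzodiazepines to implication does not fit its own drafting. Footnote d covers only the standard screen at screening, whereas Exclusion 9 also applies at baseline. And Section 6.5 has no drugs-of-abuse qualifier at all.

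Three further objections stand in full:

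- Exclusion 14b concerns ADHD only, and some ADHD drugs it would accept (atomoxetine, guanfacine, clonidine) are not on either panel. A reader might tie the benzodiazepine problem to 14b; it comes from footnote e, Section 5.7.1 and Appendix 11.1.1.
- A reader might conclude that deviation status is left undetermined. SAP 4.2 makes such cases potential important deviations only, and settles them in a review before database lock according to whether they could affect interpretation. What is missing is a single rule for that review to apply.
- FAS and safety set definitions rest on dosing and, for the FAS, on HAM-D6 data. Neither depends on eligibility, no per-protocol set appears, and no hypothesis tests or subgroup analyses are planned.

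**Conclusion.** The contradiction is real: for the same positive result, Exclusion 9 and Section 6.5 give one answer and footnote e gives the other, with no cross-reference. Section 6.5 is the more consequential part, because it acts after dosing and removes ratings. The pre-lock review in SAP 4.2 can classify a deviation, but it cannot bring back a subject who was screened out or a rating that was not taken.

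The reach is limited. It touches who is enrolled, the screen-failure and deviation outputs, consistency between sites, and the completeness of observed-case HAM-D6 data. It does not alter any analysis-set definition. For an affected dosed subject the loss is 13 of 18 post-baseline HAM-D6 ratings if withdrawn on Day 4 and 7 of 18 if withdrawn on Day 7, on a literal reading of Section 6.5. A reader might want a head count as a share of 50. The documents do not support one: subjects lost at screening come from a screened pool of unstated size, and not every permitted user will test positive, since methylphenidate is not tested after screening and benzodiazepines may be taken only as needed.

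**What to change.** Reconcile Exclusion 9 (synopsis and Section 4.2.3), Section 6.5 and Table 3 footnote e so that all state the same set of allowed positives at screening, at baseline and at later clinic visits. Section 6.5 should also say how a cannabinoid positive is handled in a subject whose use Exclusion 11 permits. Which rule prevails is for the sponsor to decide. If the exceptions are kept, they belong in Exclusion 9 and Section 6.5, either written out or by reference to footnote e. If they are dropped, footnote e and the permissions in Section 5.7.1 and Appendix 11.1.1 need matching text.

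Changing Exclusion 9 alone is not enough, because the same subject would still meet the withdrawal rule in Section 6.5 on Day 1.

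The reconciled rule should then be the one applied when potential deviations are reviewed under SAP 4.2. The cost is a few clauses in the protocol, with no added procedures, visits or tests.
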